11.7 Progression free survival (PFS)

Progression free survival will be defined as time from the initiation of protocol treatment to the occurrence of any of the following events: disease progression or disease recurrence or death from any cause. All patients surviving at the time of analyses without events will be censored at their last follow-up date.

PFS along with the confidence intervals will be estimated using the Kaplan-Meier method. Patients with local calls of disease progression (i.e. calls made by the treating institution), will be counted as having had an event, even if the central review does not declare progression. We will also report PFS based on central radiology review as a secondary analysis, if adequate number of disagreements in progressions exist between the treating institutions and the central radiology review to make such an analysis meaningful.

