8.3 Radiology Studies

8.3.1 Bone Age/Knee MRI

All tibial radiographs and knee MRIs (if obtained) should be submitted for review.

8.3.2 Central Radiology Review for Response:

Patients who respond (CR, PR) to therapy or have long term stable disease (SD) (≥ 6 cycles) on protocol therapy will be centrally reviewed. The Operations center will notify the site when a patient has met the criteria for review. The tumor disease evaluations to be submitted for review include baseline (pre-study) evaluations as well as all end of cycle tumor disease evaluations which occurred while the patient was on the subprotocol therapy study..

8.3.3 Technical Details of Submission:

To ensure an adequate interpretation of FDG-PET and CT with contrast scans, scans transferred between the treating institutions and the Imaging and Radiation Oncology Core Group IROC RI (QARC) must be submitted in Digital Imaging and Communications in Medicine (DICOM) format. BMP files, JPG files, or hard copies (films) are unacceptable for adequate interpretation of PET and CT with contrast scans. Imaging studies must be submitted electronically as outlined in the following paragraph. The images will be made available to study radiologists and nuclear medicine physicians for central review.

Submission of Diagnostic Imaging data in DICOM format is required.

Submission of the digital files and reports via TRIAD is preferred. Instructions for TRIAD set up are below.

Alternatively, the images and reports may be submitted via sFTP to IROC Rhode Island. Digital data submission instructions including instructions for obtaining a sFTP account, can be found at <http://irocri.qarc.org>. Follow the link labeled digital data. Sites using the Dicomcommunicator software to submit imaging may continue to use that application.

Corresponding Radiology reports may be submitted along with the electronic submission via TRIAD or sFTP or may be emailed to [contact]. The COG operations center and IROC are available to assist with any queries regarding the corresponding radiology reports which should be included when the scans are submitted

Questions may be directed to [contact] or [contact].

Digital RT Data Submission Using TRIAD (if TRIAD is available at your site):
TRIAD is the American College of Radiology's (ACR) image exchange

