10.2 Follow-Up Data Submission and APEC1621SC Off Study Criteria

Patients who are off subprotocol therapy will continue to be followed on the APEC1621SC screening protocol. Follow-up data submission will occur until one of the APEC1621SC Off Study Criteria is met (See Section 10 of APEC1621SC for details). Ongoing adverse events, or adverse events that emerge after the patient is removed from protocol therapy, but within 30 days of the last dose of investigational agent, must be followed and reported via RAVE and CTEP-AERS (if applicable). Follow-up data will be required until off study criteria are met unless consent is withdrawn or the patient dies or is lost to follow-up.

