Any eligible patient who is enrolled and receives at least one dose of protocol therapy will be considered evaluable for response. Any patient who receives non-protocol anti-cancer therapy during the response evaluation period will be considered a non-responder for the purposes of the statistical rule, unless they show an objective response prior to receiving the non-protocol anti-cancer therapy (in which case they will be considered a responder). Patients who demonstrate a complete or partial response confirmed by central review will be considered to have experienced a response. When opening expansion cohorts, the evaluation period for determination of best response will be 6 treatment cycles. All other patients will be considered non-responders. Patients who are not evaluable for response evaluation may be replaced for the purposes of the statistical rule. All patients considered to have a response (CR or PR) must have imaging studies reviewed centrally at the COG. Centers will be notified by the COG about requests for scans of patients with stable disease. Preliminary assessment of activity using institutionally provided tumor measurements will be entered into CDUS quarterly. The central review by COG will be provided as the final reviewed assessment of response when such becomes available.

11.6 **Evaluability for Toxicity**

All eligible patients who receive at least one dose of protocol therapy will be considered in the evaluation of toxicity.

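### PFS is censored at last follow-up rather than last disease assessment, so it can be overstated; separately, the planned central reads cannot supply a central-review PFS for the whole cohort

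*Combined protocol and SAP*

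**What the plan says.** Section 11.7 counts PFS from the start of protocol treatment to progression, recurrence or death, whatever its cause. The censoring rule is: "All patients surviving at the time of analyses without events will be censored at their last follow-up date". Section 12.2 repeats the definition in shorter form. Neither section mentions the last disease assessment.

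Progression in the main analysis is the treating institution's call. A patient with a local call "will be counted as having had an event, even if the central review does not declare progression". Section 11.7 then adds: "We will also report PFS based on central radiology review as a secondary analysis, if adequate number of disagreements in progressions exist". It puts no number on an adequate count of disagreements and gives no rule for patients who have no central read.

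Three other parts of the plan bear on this:

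- **Leaving without progression.** Section 10.1 allows removal for adverse events, refusal, non-compliance, physician decision and completion of 26 cycles. Section 10.2 then says: "Patients who are off subprotocol therapy will continue to be followed on the APEC1621SC screening protocol".
- **Assessments.** Tumor evaluation is at the end of cycles 2, 4 and 6, then every 3 cycles, while on therapy. After removal in a cycle later than the first, Section 10.1 asks only for the observations that clinical care needs.
- **Central review.** Section 8.3.2 says: "Patients who respond (CR, PR) to therapy or have long term stable disease (SD) (≥ 6 cycles) on protocol therapy will be centrally reviewed". For these patients the sites send the baseline studies and "all end of cycle tumor disease evaluations which occurred while the patient was on the subprotocol therapy study". Section 11.5 adds: "Centers will be notified by the COG about requests for scans of patients with stable disease".

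**The concern.** A Kaplan-Meier curve for PFS treats each patient as known to be progression-free up to the censoring date. If that date is a contact at which the patient was only known to be alive, the patient stays in the risk set, event-free, over time when progression could have happened unseen. The patients exposed to this are those who stop without progression and are then followed under another protocol.

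PFS is the first secondary aim, and the trial has a single arm. The curve is the whole PFS result, and no control group shares the error and cancels it.

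The central-review PFS raises a different problem. Review is triggered by doing well: a response, or stable disease for 6 cycles. Patients who progress early without responding have no planned central read, so central dates do not exist for the whole cohort. The trigger for reporting the analysis, disagreement between local and central progression, can be seen only in the reviewed group.

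**Working it through.** The plan states no PFS median, rate or event count, so there is no figure of its own to reproduce. Everything below is illustrative and rests on the assumptions listed.

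**1. Censoring rule, closed form**

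From the plan: the first tumor evaluation is at the end of cycle 2 (56 days, taken as t0 = 1.85 months). Assumed: exponential true PFS with median m, so S(t) = 2^(−t/m). A share q of patients still event-free at t0 leaves then, for reasons unrelated to prognosis. A share c of the leavers' later events is captured at the true date. The rest are contacted past month 6 with nothing recorded.

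Let r = S(6)/S(t0). Under last-follow-up censoring the expected 6-month estimate is S(t0) × [q(1−c) + (1 − q(1−c)) × r]. The truth is S(t0) × r, so the excess is

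E = S(t0) × q × (1−c) × (1−r).

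For m = 4: S(1.85) = 0.7257, S(6) = 0.3536, r = 0.4872. With q = 0.2 and c = 0, E = 0.7257 × 0.2 × 0.5128 = 0.074.

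For m = 2: S(1.85) = 0.5267, S(6) = 0.1250, r = 0.2373. With q = 0.2 and c = 0, E = 0.5267 × 0.2 × 0.7627 = 0.080.

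| Median | True 6-month PFS | c = 0 | c = 0.5 | c = 1 |
|---|---|---|---|---|
| 2 months | 12.5% | 20.5% | 16.5% | 12.5% |
| 4 months | 35.4% | 42.8% | 39.1% | 35.4% |

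Halving q has the same effect as c = 0.5. If leavers are censored at t0 instead, the expected estimate is the true value under these assumptions.

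**2. Censoring rule, simulation on the plan's scan schedule**

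20,000 patients per scenario; medians 2, 4 and 8 months; 10–30% stopping before progression; last contact 3 or 12 months after stopping; 30% of progressions found clinically at onset. This is a separate set-up, so compare direction and order of size with part 1, not single figures.

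- Median 4, 20% stopping, 12-month contact, nothing captured: 6-month PFS is 45.1% with last-follow-up censoring, 37.0% with last-assessment censoring and 37.6% with complete ascertainment. At 12 months the figures are 29.6%, 14.1% and 14.3%.
- All scenarios, nothing captured: the 6-month excess is +0.7 to +27 points.
- Half captured, 12-month contact: +0.6 to +13 points.
- Everything captured: 0.
- Last-assessment censoring stayed within about 1.2 points of complete ascertainment.

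**3. Central-review PFS**

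Assumed: objective response rate 5% or 25%; the central date differs by one scan in 20% of reviewed patients with progression. The table gives 6-month PFS under three possible ways to treat unreviewed patients.

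| Median, response rate | Local calls, all patients | Share reviewed | Reviewed only | Unreviewed censored at local PD | Local dates kept |
|---|---|---|---|---|---|
| 2 months, 5% | 15.8% | 18.8% | 84.5% | 92.4% | 14.2–16.2% |
| 2 months, 25% | 20.8% | 36.3% | 57.3% | 69.7% | 18.5–22.6% |
| 4 months, 5% | 39.4% | 41.2% | 95.5% | 97.0% | 36.2–39.6% |
| 4 months, 25% | 43.7% | 53.2% | 82.1% | 86.1% | 40.5–44.9% |
| 8 months, 5% | 63.0% | 64.0% | 98.5% | 98.8% | 60.4–63.1% |
| 8 months, 25% | 66.1% | 71.3% | 92.7% | 93.7% | 63.4–66.8% |

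The reviewed-only column can be checked by hand. Six cycles are 168 days, about 5.5 months, so a patient on therapy and progression-free at 6 months has qualified for review. The reviewed-only figure is then the local figure divided by the share reviewed: 39.4/41.2 = 95.6% and 43.7/53.2 = 82.1%.

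With local dates kept, the change from the local result runs from −3.2 points (36.2 against 39.4) to +1.8 points (22.6 against 20.8).

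**The case against.** A reader might infer that both features bias PFS upward. The documents do not support that.

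On censoring, follow-up off therapy is governed by APEC1621SC, which is not among these documents. Section 10.2 requires follow-up data until that protocol's off-study criteria are met. PFS counts progression, recurrence or death at any time, not only on therapy. Under Section 8.1, progression in solid tumors may be called on clinical or laboratory grounds without a scan. A contact can therefore be a real assessment, and deaths that are recorded limit the error. With complete capture the stated rule is correct. This stands in full: the bias is possible, and its size is unknown. The assumption that nothing is captured is an upper case.

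On precision, with 20 patients the standard error of a 6-month rate between 12.5% and 35% is about 7 to 11 points (√(0.125 × 0.875/20) = 0.074; √(0.35 × 0.65/20) = 0.107). An excess of 4 to 8 points is about one standard error or less. That is true, but the excess moves the estimate in one direction and the confidence interval does not reflect it.

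On central review, selection cannot affect the main PFS, which uses local calls for everyone. Section 11.7 does not say that unreviewed patients are dropped, and keeping their local dates gives a whole-cohort estimate. Central reading also reaches somewhat further than Section 8.3.2: Section 12.5.3 has MIBG response in neuroblastoma read centrally without limiting it to responders, and Section 11.5 allows requests for scans of stable disease. These widen the reviewed group but do not cover early progressors in general. A progression called without a scan leaves no image to review.

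**Conclusion.** The point holds as a conditional one.

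- **Censoring.** The rule can overstate PFS to the extent that follow-up runs past the last assessment without capturing progression. With 20% leaving at the end of cycle 2, a median of 2 or 4 months and nothing captured, the excess at 6 months is 7 to 8 points. With half captured it is about 4 points, and with full capture zero. The leaving rate, the median and the capture rate are all assumptions.
- **Central-review PFS.** As planned, it cannot be derived from central reads for the whole cohort. What it would show depends on a rule that Section 11.7 does not give: 57% to 99% at 6 months on reviewed patients only, against 16% to 66% by local calls, or a shift of −3.2 to +1.8 points if local dates are kept. The defect is an undefined analysis, not a demonstrated upward bias.

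PFS is a secondary estimate with no threshold. The decision rule of at least 3 responses in 20 is unaffected by either part. The change is worth making because it is cheap and protects the only PFS result that the trial will report.

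**What to change.** In Section 11.7, censor event-free patients at the last disease assessment that documents no progression. Count imaging, and clinical assessment where the protocol allows it. Censor at the start of treatment if there is no such assessment. Keep last-follow-up censoring as a sensitivity analysis; the gap between the two estimates shows how much rests on unassessed time.

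Replace the conditional central-review Kaplan-Meier estimate with a listing of local and central progression dates in the patients actually reviewed. Alternatively, keep local dates for unreviewed patients, say so, and label the analysis as local dates with central substitution where available.

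The cost is mainly wording. The stated PFS may be slightly lower. Assessment dates after therapy must be available from APEC1621SC follow-up, which these documents do not confirm. Last-assessment censoring also assumes that leaving is unrelated to prognosis, so the number of patients leaving without progression, and their reasons, should be reported beside the curve.

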11.8 Correlative Studies

A descriptive analysis of the exploratory aims described in [Section 1.3](#) will be performed and will be summarized with simple summary statistics. All of these analyses will be descriptive in nature.

11.9 Gender and Minority Accrual Estimates

The gender and minority distribution of the study population is expected to be:

Racial category	Ethnicity				Total
	Not Hispanic or Latino		Hispanic or Latino		
	Female	Male	Female	Male	
American Indian/Alaska Native	0	0	0	0	0
Asian	1	1	0	0	2
Native Hawaiian or Other Pacific Islander	0	0	0	0	0
Black or African American	3	5	0	0	8
White	12	20	4	2	38
More than one race	1	0	0	0	1
Total	17	26	4	2	49

This distribution was derived from the demographic data for patients enrolled on recent COG Phase 2 trials.

12.0 EVALUATION CRITERIA

12.1 Common Terminology Criteria for Adverse Events (CTCAE)

The descriptions and grading scales found in the current version of the NCI Common Terminology Criteria for Adverse Events (CTCAE) v5.0 will be utilized for AE reporting. All appropriate treatment areas should have access to a copy of the current CTCAE V 5.0. A copy of the CTCAE V 5.0 can be downloaded from the CTEP website (<http://ctep.cancer.gov>).

12.2 Progression-Free Survival

Progression-free survival (PFS) is defined as the duration of time from start of subprotocol treatment to time of progression or death, whichever occurs first.

Development of new disease or progression in any established lesions is considered progressive disease, regardless of response in other lesions – e.g., when multiple lesions show opposite responses, the progressive disease takes precedence.

12.3 Response Criteria for Patients with Solid Tumors

See the table in [Section 8.0](#) for the schedule of tumor evaluations. Eligible patients must have measurable disease present at baseline and have had their disease re-evaluated after one dose of protocol therapy. In addition to the scheduled scans, a confirmatory scan should be obtained on the next consecutive cycle following initial documentation of objective response.

As outlined, patients will be assigned to one of the following categories for assessment of response: a) solid tumor (non-CNS) and measurable disease ([Section 12.4](#)); b) neuroblastoma with MIBG positive lesions ([Section 12.5](#)); c) CNS tumor ([Section 12.7](#)); and d) non-Hodgkin lymphoma/histiocytosis ([Section 12.8](#)). Note: Neuroblastoma patients who do not have MIBG positive lesions should be assessed for response as solid tumor patients with measurable disease.

Response and progression will be evaluated in this study using the revised Response Evaluation Criteria in Solid Tumors (RECIST) guideline (version 1.1) [*Eur J Ca* 45:228-247, 2009]. Key points are that 5 target lesions are identified and that changes in the *largest* diameter (unidimensional measurement) of the tumor lesions but the *shortest* diameter of malignant lymph nodes are used in the RECIST v 1.1 criteria.

12.3.1 Definitions

12.3.1.1 Evaluable for objective response: Eligible patients who receive at least one dose of protocol therapy will be considered evaluable for response. Evaluable patients who demonstrate a complete or partial response confirmed by central review before receiving non-protocol anti-cancer therapy will be considered a responder. All other evaluable patients will be considered non-responders.

12.3.1.2 Evaluable Non-Target Disease Response: Eligible patients who have lesions present at baseline that are evaluable but do not meet the definitions of measurable disease and have received at least one dose of protocol therapy will be considered evaluable for non-target disease. The response assessment is based on the presence, absence, or unequivocal progression of the lesions.

12.3.2 Disease Parameters

12.3.2.1 Measurable disease: Measurable lesions are defined as those that can be accurately measured in at least one dimension (longest diameter to be recorded) as ≥ 20 mm by chest x-ray, as ≥ 10 mm with CT scan, or ≥ 10 mm with calipers by clinical exam. All tumor measurements must be recorded in millimeters (or decimal fractions of centimeters).

Note: Tumor lesions that are situated in a previously irradiated area might or might not be considered measurable. If the investigator thinks it appropriate to include them, the conditions under which such lesions should be considered must be defined in the protocol.

12.3.2.2 Malignant lymph nodes: To be considered pathologically enlarged and measurable, a lymph node must be ≥ 15 mm in short axis when assessed by CT scan (CT scan slice thickness no greater than 5 mm). At baseline and in follow-up, only the short axis will be measured and followed.

12.3.2.3 Non-measurable disease: All other lesions (or sites of disease), including small lesions (longest diameter < 10 mm or pathological lymph nodes with ≥ 10 to < 15 mm short axis), are considered non-measurable disease. Bone lesions, leptomeningeal disease, ascites, pleural/pericardial effusions, lymphangitis cutis/pulmonitis, inflammatory breast disease, and abdominal masses (not followed by CT or MRI), are considered as non-measurable.

Note: Cystic lesions that meet the criteria for radiographically defined simple cysts should not be considered as malignant lesions (neither measurable nor non-measurable) since they are, by definition, simple cysts. 'Cystic lesions' thought to represent cystic metastases can be considered as measurable lesions, if they meet the definition of measurability described above. However, if non-cystic lesions are present in the same patient, these are preferred for selection as target lesions.

12.3.2.4 Target lesions: All measurable lesions up to a maximum of 2 lesions per organ and 5 lesions in total, representative of all involved organs, should be identified as target lesions and recorded and measured at baseline. Target lesions should be selected on the basis of their size (lesions with the longest diameter), be representative of all involved organs, but in addition should be those that lend themselves to reproducible repeated measurements. It may be the case that, on occasion, the largest lesion does not lend itself to reproducible measurement in which circumstance the next largest lesion that can be measured reproducibly should be selected. A sum of the diameters (longest for non-nodal lesions, short axis for nodal lesions) for all target lesions will be calculated and reported as the baseline sum diameters. If lymph nodes are to be included in the sum, then only the short axis is added into the sum. The baseline sum diameters will be used as reference to further characterize any objective tumor regression in the measurable dimension of the disease.

12.3.2.5 Non-target lesions: All other lesions (or sites of disease) including any measurable lesions over and above the 5 target lesions should be identified as non-target lesions and should also be recorded at baseline. Measurements of these lesions are not required, but the presence, absence, or in rare cases unequivocal progression of each should be noted throughout follow-up.

12.3.3 Methods for Evaluation of Measurable Disease

All measurements should be taken and recorded in metric notation using a ruler or calipers.

The same method of assessment and the same technique should be used to characterize each identified and reported lesion at baseline and during follow-up. Imaging-based evaluation is preferred to evaluation by clinical examination unless the lesion(s) being followed cannot be imaged but are assessable by clinical exam.

- 12.3.3.1 Clinical lesions: Clinical lesions will only be considered measurable when they are superficial (e.g., skin nodules and palpable lymph nodes) and ≥ 10 mm diameter as assessed using calipers (e.g., skin nodules). In the case of skin lesions, documentation by color photography, including a ruler to estimate the size of the lesion, is recommended.
- 12.3.3.2 Chest x-ray: Lesions on chest x-ray are acceptable as measurable lesions when they are clearly defined and surrounded by aerated lung. However, CT is preferable.
- 12.3.3.3 Conventional CT and MRI: This guideline has defined measurability of lesions on CT scan based on the assumption that CT slice thickness is 5 mm or less. If CT scans have slice thickness greater than 5 mm, the minimum size for a measurable lesion should be twice the slice thickness. MRI is also acceptable in certain situations (e.g. for body scans). Ideally, the same type of scanner should be used and the image acquisition protocol should be followed as closely as possible to prior scans.
- 12.3.3.4 PET-CT: At present, the low dose or attenuation correction CT portion of a combined PET-CT is not always of optimal diagnostic CT quality for use with RECIST measurements. However, if the site can document that the CT performed as part of a PET-CT is of identical diagnostic quality to a diagnostic CT (with IV and oral contrast), then the CT portion of the PET-CT can be used for RECIST or International Pediatric non-Hodgkin Lymphoma Response Criteria measurements and can be used interchangeably with conventional CT in accurately measuring cancer lesions over time. Note, however, that the PET portion of the CT introduces additional data which may bias an investigator if it is not routinely or serially performed.
- 12.3.3.5 Tumor markers: Tumor markers alone cannot be used to assess response. If markers are initially above the upper normal limit, they must normalize for a patient to be considered in complete clinical response.
- 12.3.3.6 Cytology, Histology: These techniques can be used to differentiate between partial responses (PR) and complete responses (CR) in rare cases (e.g., residual lesions in tumor types, such as germ cell tumors, where known residual benign tumors can remain).

Cytology should be obtained if an effusion appears or worsens during treatment when the measurable tumor has met criteria for response or stable disease.

12.3.3.7 **FDG-PET:** While FDG-PET response assessments need additional study, it is sometimes reasonable to incorporate the use of FDG-PET scanning to complement CT scanning in assessment of progression (particularly possible 'new' disease). New lesions on the basis of FDG-PET imaging can be identified according to the following algorithm:

- a. Negative FDG-PET at baseline, with a positive FDG-PET at follow-up is a sign of PD based on a new lesion.
- b. No FDG-PET at baseline and a positive FDG-PET at follow-up: If the positive FDG-PET at follow-up corresponds to a new site of disease confirmed by CT, this is PD. If the positive FDG-PET at follow-up is not confirmed as a new site of disease on CT, additional follow-up CT scans are needed to determine if there is truly progression occurring at that site (if so, the date of PD will be the date of the initial abnormal FDG-PET scan). If the positive FDG-PET at follow-up corresponds to a pre-existing site of disease on CT that is not progressing on the basis of the anatomic images, this is not PD.

Note: A 'positive' FDG-PET scan lesion means one that is FDG avid with an uptake greater than twice that of the surrounding tissue on the attenuation corrected image.

For patients with a positive PET scan at diagnosis, PET can be used to follow response in addition to a CT scan using the International Pediatric non-Hodgkin Lymphoma Response Criteria.¹⁰

